10.2 Populations for Analyses

The analysis populations will consist of participants as defined in [Table 10–1](#).

Table 10–1 Analysis Populations

Population	Definition
Screened	All participants who sign informed consent
Intent-to-treat (ITT)	All randomized participants
Modified intent-to-treat (mITT)	All randomized participants with ≥ 1 postbaseline assessment of DGSSD
Safety	All participants who received ≥ 1 administration of study treatment

10.3 Statistical Analyses

The statistical analysis plan (SAP) will be developed and finalized before database lock and will describe the participant populations to be included in the analyses, and procedures for accounting for missing data. This section is a summary of the planned statistical analyses of the key endpoints.

10.3.1 Key Statistical Methodology

The methodologies defined in [Table 10–2](#) apply as specified to individual endpoints defined in the SAP. All statistical tests will be 2-sided hypothesis tests performed at the 5% level of significance for main effects. All CIs will be 2-sided 95% CIs, unless stated otherwise.

Table 10–2 Statistical Methodology

Methodology	Description
Categorical counts	
 • Number of participants in individual categories 
 ○ Participants with ≥ 1 qualifying event counted once per individual category
Categorical descriptives	
 • Number and percentage of participants in individual categories 
 ○ Participants with ≥ 1 qualifying event counted once per individual category • N1 if percentage denominator \neq number of participants in the population (standard percentage denominator) 
 ○ N1 = participants with nonmissing baseline value
Continuous descriptives	
 • N1, mean, SD, median, minimum, maximum • N1 = participants with nonmissing value
CFB descriptives	
 • Continuous descriptives for baseline, postbaseline, and change from baseline (CFB) values • N1 = participants with nonmissing values at both baseline and the specified postbaseline analysis visit
CFB MMRM	
 • Continuous descriptives and standard error (SE) for baseline, postbaseline, and CFB values 
 ○ Estimates derived from mixed model for repeated measures (MMRM) for CFB value controlling for factors (treatment group, site) and covariates (baseline value) 
 ▪ Least squares (LS) means and standard errors ▪ LS mean differences, standard errors, and CIs vs placebo ▪ P-values from contrast t-test comparing treatment group vs placebo • N1 = participants with nonmissing values at both baseline and the specified postbaseline analysis visit

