Approximately 5000 participants will be screened in lead-in Studies RLM-MD-01 and RLM-MD-02. Participants who do not meet certain randomization criteria may enter this study directly if they meet enrollment criteria defined below.

Study Population:

Two different groups of participants may enter the study:

- Participants who met all Screening and Run-in Period criteria in lead-in Study RLM-MD-01 or lead-in Study RLM-MD-02 (including compliance with dosing and data entry into the Diabetic Gastroparesis Symptom Severity Diary [DGSSD] during the lead-in study Run-in Period), but were not randomization-eligible at the end of the lead-in study Run-in Period, are eligible for randomization in Study RLM-MD-04 if:
 - They had no vomiting episodes recorded in the DGSSD and had an average daily DGSSS ≥ 12 at the end of the lead-in study Run-in Period.

OR

- They had vomiting episodes recorded in the DGSSD but had an average daily DGSSS of ≥ 12 and < 16 at the end of the lead-in study Run-in Period.

In the current study, these “**rollover participants**” will enter the study at Visit 1 (Randomization); they will not undergo Screening (Visit -2) or Run-in Visit (Visit -1) procedures.

2. Patients who undergo screening and run-in procedures in Study RLM-MD-04 are “**de novo participants**”. To be eligible for randomization in the current study, de novo participants must meet all Screening and Run-in Period criteria for Study RLM-MD-04, including:

At the Screening Visit (Visit -2):

- Male or female aged 18 years and older;
- T1DM or T2DM with controlled and stable blood glucose levels and HbA1c $\leq 11\%$;
- Symptoms suggestive of DG for at least 3 months (one of which must be nausea), with mechanical obstruction of the gastrointestinal (GI) tract as the cause of symptoms having been ruled out;
- History of nausea and/or at most a single episode of vomiting in the 2 weeks prior to Screening (Visit -2), as ascertained by participant history

[figure not shown]
At the End of the Run-in Period:

- Evidence of compliance during the Run-in Period with both the use of the electronic hand-held device for entry of data and with twice daily SC injections of the study treatment;
- No treatment with GI promotility agents during the Run-in Period;
- A score of ≥ 12 for the average of the daily DGSSS measured during the Run-in Period.

[figure not shown]
Number of Sites:

Approximately 700 sites globally (the combined number of sites from Studies RLM-MD-01 and RLM-MD-02).

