5.2 Participant and Study Completion

Approximately 5000 participants will be screened in lead-in Studies RLM-MD-01 and RLM-MD-02. Certain participants who were not eligible for randomization at the end of the lead-in study Run-in Period (rollover participants) may enter this study (see Section 5.1 for rollover participant eligibility criteria).

In addition, participants who undergo Screening and Run-in Visit procedures will be eligible for randomization if they meet all inclusion/exclusion criteria for the current study (see Sections 6.1.2 and 6.2.3 for de novo participant eligibility criteria).

The goal is to achieve 600 participants assigned to study treatment (400 to relamorelin and 200 to placebo). A total of 300 participants are expected to complete the study (200 treated with relamorelin and 100 with placebo). See Section 10.1 for details on sample size determination.

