7.3 Method of Treatment Assignment

All participants will be centrally assigned to randomized study treatment using an interactive web response system (IWRS). Before the study is initiated, the log-in information and directions for the IWRS will be provided to each site.

At the beginning of the 52-week Treatment Period, participants will be randomized in a 2:1 ratio to blinded treatment with relamorelin 10 µg or placebo.

Study treatment will be dispensed at the study visits indicated in the SoA (Section 2).

Returned study treatment should not be re-dispensed to the participants.

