The main efficacy assessment is the Diabetic Gastroparesis Symptom Severity Diary (DGSSD), a 7-item, patient-reported daily diary designed to assess the severity of 6 core signs and symptoms of DG—nausea, abdominal pain, postprandial fullness, bloating, vomiting, and early satiety—and the frequency of vomiting episodes. The severity of DG symptoms are assessed using a 0 to 10 numerical rating scale (NRS), on which 0 = “no” or “not at all uncomfortable” (ie, absence of the DG symptom) and 10 = “worst possible” or “most uncomfortable” (ie, worst experience of the DG symptom).

The Diabetic Gastroparesis Symptom Severity Score (DGSSS) is an overall assessment of the severity of non-vomiting symptoms. It is the sum of the four individual DGSSD items of nausea, abdominal pain, postprandial fullness and bloating. The score ranges from 0 to 40.

Participants report their symptoms daily from Visit 1/Baseline to Visit 4/Week 12, and for each of the 4 weeks preceding Visits 5/Week 24, Visit 6/Week 36, and Visit 7/Week 52 in the DGSSD.

Baseline values for DGSSD based parameters are derived from the DGSSD assessment collected during the Run-in Period as the average of the two weekly values of Week -2 and Week -1.

There are two key efficacy endpoints as follows:

Key Endpoints	Description	Timing
CFB to Week 12 in weekly DGSSS	Change from baseline to Week 12 in weekly DGSSS	Week 12
CFB to Week 52 in weekly average DGSSS	Change from baseline in average of the weekly average DGSSS from Weeks 49 to 52	Week 49-Week 52

Since the study was early terminated, only descriptive analyses for the key efficacy endpoints will be performed.

11.0 **Safety Analyses**

The safety analysis will be performed using the Safety Population. The safety parameters will include adverse events (AEs), clinical laboratory, electrocardiogram, vital sign parameters.

11.1 **Adverse Events**

All AEs and serious AEs (SAEs) will be collected from the signing of the informed consent form (ICF) until 30 days after the final visit in the study (Visit 7) or Early Termination Visit at the time points specified in the SoA. For rollover participants, ongoing AEs from lead-in Studies RLM-MD-01 and RLM-MD-02, and new AEs that occur after the signing of the ICF for RLM-MD-04 are considered to be AEs in RLM-MD-04.

Adverse events will be coded by system organ class and preferred term using the *Medical Dictionary for Regulatory Activities (MedDRA)*, version 23.0 or newer.

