11.5 COVID-19

A listing of participants with visits impacted due to COVID-19 for the ITT population will be provided.

12.0 **Interim Analysis**

There is no interim analysis planned for this study.

13.0 **Determination of Sample Size**

The study is early terminated; and the original study primary objectives are no longer applicable. The original study design of this protocol is for those participants who screen failed either of the two pivotal registration studies (ie, Studies RLM-MD-01 and RLM-MD-02). The original study design was to achieve 600 participants from these screen failures (assuming approximately 2800 participants will be screened for the two pivotal studies together) who will be randomized in a 2:1 ratio (for Relamorelin vs Placebo) to this study. For the originally designed two primary endpoints (original protocol dated October 6, 2017, amendments #1 and #2 dated December 20, 2017 and March 29, 2018, respectively), 600 randomized participants would provide at least 90% power for both the 4-symptom composite DGSSS responder endpoint (assuming a placebo rate of 14% and a treatment rate of 35%) and the vomiting responder endpoint (assuming a placebo rate of 11% and a treatment rate of 26%). For the redesigned key efficacy endpoint, change from baseline in 4-symptom DGSSS composite score at Week 12 (Protocol amendment #3 dated April 29, 2019), the planned sample size of 600 participants would provide more than 90% power in detecting a clinical meaningful difference, assuming Relamorelin provides additional 3.8 points of improvement as compared to Placebo.

14.0 **Statistical Software**

Statistical analyses will be performed using version 9.4 (or newer) of SAS on a Linux operating system.

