The study was early terminated and only an abbreviated study report will be applied to this study, for which only minimum efficacy analyses will be implemented. As such, this document is an abbreviated statistical analysis plan for only selected study disposition, demographics, safety parameters and selected descriptive efficacy analyses.

17.0 **References**

There are no references.

Electronic Signatures

User	Date	Justification
[REDACTED]	16-Dec-2020 01:23:35 (GMT)	Document Originator Approval
[REDACTED]	15-Dec-2020 20:23:50 (GMT)	Manager Approval
[REDACTED]	15-Dec-2020 20:29:15 (GMT)	Subject Matter Expert Approval
[REDACTED]	15-Dec-2020 21:16:33 (GMT)	Subject Matter Expert Approval
[REDACTED]	15-Dec-2020 21:51:48 (GMT)	Subject Matter Expert Approval

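### Does listing site as an MMRM factor, with about 700 planned sites and 600 participants, call for a change to the plan?

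*Protocol*

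**What the plan says.** Table 10-2 in Protocol Section 10.3.1 gives the model: "Estimates derived from mixed model for repeated measures (MMRM) for CFB value controlling for factors (treatment group, site) and covariates (baseline value". Table 10-3 in Section 10.3.2.1 assigns it to both key endpoints, the Week 12 weekly DGSSS and the Week 49–52 average.

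The Synopsis plans "Approximately 700 sites globally (the combined number of sites from Studies RLM-MD-01 and RLM-MD-02", and Section 5.2 sets the size: "The goal is to achieve 600 participants assigned to study treatment (400 to relamorelin and 200 to placebo". On assignment, Section 7.3 says "All participants will be centrally assigned to randomized study treatment using an interactive web response system (IWRS", and Appendix 9 records no stratification factor. The only statement on pooling sites, in Section 5.1, joins IND with non-IND sites; it is not a rule for small sites. Section 10.3 describes its own status: "This section is a summary of the planned statistical analyses of the key endpoints".

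The SAP postdates the early termination of 04 September 2020 (SAP Section 4.0). Its Section 10.0 says: "Since the study was early terminated, only descriptive analyses for the key efficacy endpoints will be performed". Section 13.0 adds that "the original study primary objectives are no longer applicable", and Section 16.0, on departures from the protocol, that "only minimum efficacy analyses will be implemented". The SAP contains no MMRM and no site term.

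**The concern.** Site stands beside treatment group as a factor, so a fixed effect with one parameter per site is a natural reading. A random effect is also possible in a mixed model. With 600/700 = 0.86 participants per planned site, the choice could matter. Under a fixed, unpooled fit, a site with one participant or one arm tells little about the treatment difference.

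The stake is precision, not bias, because central assignment without stratification keeps treatment independent of site. Two analysts could fit different models from the same sentence, and one of them would report a wider confidence interval.

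**Working it through.** **Plan's own power figures.** Protocol Section 10.1 states 90% power for two responder endpoints (SAP Section 13.0: at least 90%). With 200 placebo and 400 relamorelin participants and a two-sided 5% test:
- 11% vs 26%: pooled rate (22+104)/600 = 0.21; null SE √(0.21×0.79×0.0075) = 0.0353; alternative SE √(0.11×0.89/200 + 0.26×0.74/400) = 0.0312. Power = Φ((0.15 − 1.96×0.0353)/0.0312), about 99.5%.
- 14% vs 35%: the same formula gives above 99.9%.

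So at least 90% is true as a lower bound. These figures contain no site term and do not bear on the question.

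**Step 1: occupied sites if enrolment is even.** Expected occupied sites = S(1 − (1 − 1/S)^600).
- S = 700 (planned count): about 403 occupied, about 255 of them with one participant.
- S = 150 (an assumption; the number of randomising sites is not given): about 147 occupied.

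**Step 2: information kept at a single visit with site fixed.** r = (N − occupied)/(N − 1).
- 700 sites: (600 − 403)/599 = 0.329.
- 150 sites: (600 − 147)/599 = 0.756.

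**Step 3: repeated measures.** SAP Table 15.1.1–1 has 24 treatment weeks (12 + 4 + 4 + 4). Assume complete data, week and treatment-by-week terms (Table 10-2 lists neither), and no true site variance. A site main effect shifts all weeks equally, so it competes only with the participant's 24-week mean. Under compound symmetry with correlation ρ, that mean carries the share b = ρ + (1 − ρ)/24 of the Week 12 variance. The variance ratio is b/r + (1 − b), and loss = 1 − 1/ratio.

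| Sites | ρ | b | Ratio | Week 12 loss |
|---|---|---|---|---|
| 150 | 0.5 | 0.521 | 1.168 | 14% |
| 150 | 0.8 | 0.808 | 1.260 | 21% |
| 700 | 0.5 | 0.521 | 2.063 | 52% |
| 700 | 0.8 | 0.808 | 2.649 | 62% |

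A numerical generalised least squares calculation over random allocations agrees: 14.2%, 21.0%, 51.6% and 62.5%. With AR(1) correlation of 0.90–0.95 per week it gives 8–12% at 150 sites and 37–48% at 700. The overall range is 8–21% and 37–63%. Confidence-interval widening is 1/√(1 − loss) − 1: 4–13% at 150 sites and 26–63% at 700.

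**Step 4: what shrinks the loss.**
- Uneven enrolment: at 700 sites, one uneven pattern keeps 54% of single-visit information instead of 33%. Then the ratio is 0.521/0.54 + 0.479 = 1.444 (ρ = 0.5) or 0.808/0.54 + 0.192 = 1.689 (ρ = 0.8). The losses are 31% and 41%, and the interval is 20–30% wider.
- True site differences: against a random-site fit with site ICC 0.05–0.20 (compound symmetry), the net loss is 5–18% at 150 sites and 35–61% at 700.
- Pooling into four to eight regions costs 0.2–1.0%.

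**Step 5: power for 3.8 points (SAP Section 13.0).** No SD is stated. Without a site term, 90% power holds for SD up to 3.8/((1.96 + 1.2816)×√(1/200 + 1/400)) = 13.5. At a 63% loss, power = Φ(3.8×√(133.3×0.37)/SD − 1.96), where 133.3 = 400×200/600: about 92% at an assumed SD of 8 and 76% at 10. At a 21% loss and SD 10 it is about 97%. The answer turns on an SD and a site count that the documents do not give.

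**The case for a change.** The best case for acting is that the protocol text still specifies this model for both key endpoints, that a fixed unpooled fit is a natural reading, and that one clause would settle it, by making site random or replacing it with pooled regions. The textual gap is real, and if the model were fitted in a supplementary analysis the interval could widen noticeably.

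The rest of the case does not carry to a change:
- Neither document mentions a supplementary MMRM. One would use data from a trial stopped early, with a randomised number and site count that are not given, so losses computed for 600 participants with complete data would not describe it.
- The table is visibly shorthand. It also omits visit, treatment-by-visit and the covariance structure, so settling the site term alone would not make two analysts agree.
- Region appears in the SAP only as a demographic (Section 8.0), so naming pooled regions without defining them would open a new ambiguity.
- The 700 sites are the combined lead-in sites. Spreading participants evenly over all of them is an extreme, not a forecast.

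**Conclusion.** No change to the plan. The site term is under-specified, but the protocol section is a summary, and an analyst writing a full SAP would be expected to make site random or pool small sites. Termination removed the need for that SAP, and the current one reports the key efficacy endpoints descriptively, so no planned result would differ.

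The size is conditional on a model nobody plans to run, fitted with site fixed and unpooled: 8–21% of Week 12 information at an assumed 150 evenly used sites, and 37–63% at the even-spread extreme of 700. Both assume 600 participants, complete data, added week terms and no true site variance. It would be a loss of precision only. No shortfall against the stated power is shown, and none can be shown or excluded without an SD.

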10.3.2 Efficacy Analyses

10.3.2.1 Key Endpoints

Table 10–3 displays the key efficacy endpoints that will be analyzed for the mITT population. All other efficacy endpoints and analyses will be defined in the SAP.

Table 10–3 Key Endpoints

Key Endpoints	Description	Timing	Methodology
Key Endpoints			
CFB to Week 12 in weekly DGSSS	Change from baseline to Week 12 in weekly DGSSS	Week 12	CFB MMRM
CFB to Week 52 in weekly average DGSSS	Change from baseline in average of the weekly average DGSSS from Weeks 49 to 52	Week 49-Week 52	CFB MMRM

10.3.2.2 Missing Data

[figure not shown]
Handling of missing data will be provided in the SAP.

10.3.3 Safety Analyses

All safety analyses will be performed on the Safety Population.

The following safety categories will be summarized as appropriate (eg, categorical or continuous descriptives, shift tables) for the safety population and will be fully defined in the SAP.

- AEs
 - Clinically significant hyperglycemia- and hypoglycemia-related events
- Clinical laboratory assessments
 - Hy's law cases
- Vital signs
- ECGs
- Study-specific assessments
 - HbA1c

10.3.5 Interim Analyses

In addition to the above, monitoring of participant safety data will be performed by an independent Data and Safety Monitoring Board (DSMB). The DSMB will review interim safety data at defined intervals throughout the study. The DSMB will communicate their recommendations to the Sponsor after each meeting, but will serve in an advisory capacity only; the Board will not be empowered to stop the study or require changes to the protocol. Study conduct may be interrupted or terminated by the Sponsor based on DSMB recommendations if safety data become available that appear to represent an undue risk to the study participants' health or well being. Further details of the DSMB (composition, policy, and procedures) are specified in a separate DSMB charter.

11 References

All references are available upon request.

Bharucha AE. Epidemiology and natural history of gastroparesis. *Gastroenterol Clin North Am*. 2015;44(1):9-19.

Centers for Disease Control and Prevention. *Measuring Healthy Days*. Atlanta, Georgia: CDC, November 2000.

de la Loge C, Trudeau E, Marquis P, et al. Cross-cultural development and validation of a patient self-administered questionnaire to assess quality of life in upper gastrointestinal disorders: the PAGI-QOL. *Qual Life Res*. 2004;13(10):1751-1762.

de la Loge C, Trudeau E, Marquis P, et al. Responsiveness and interpretation of a quality of life questionnaire specific to upper gastrointestinal disorders. *Clin Gastroenterol Hepatol*. 2004;2(9):778-86.

Dornonville de la Cour C, Lindström E, Norlén P, et al. Ghrelin stimulates gastric emptying but is without effect on acid secretion and gastric endocrine cells. *Regul Pept*. 2004;120(1-3):23-32.

12.1 Appendix 1: Abbreviations and Trademarks

ADA	anti-drug antibodies
AE	adverse event
AESI	adverse event of special interest
ALT	alanine aminotransferase
AST	aspartate aminotransferase
BID	twice daily
BMI	body mass index
BP	blood pressure

[figure not shown]
CDER	Center for Drug Evaluation and Research
CFB	change from baseline
CFR	Code of Federal Regulations
CIOMS	Council for International Organizations of Medical Sciences
CONSORT	Consolidated Standards of Reporting
CSR	clinical study report
DG	diabetic gastroparesis
DGSSD	Diabetic Gastroparesis Symptom Severity Diary
DGSSS	Diabetic Gastroparesis Symptom Severity Score
DILI	drug-induced liver injury
DSMB	Data and Safety Monitoring Board
ECG	electrocardiogram

eCRF	electronic case report form
eGFR	estimated glomerular filtration rate
FDA	US Food and Drug Administration
FSH	follicle stimulating hormone
GCP	Good Clinical Practice

GE	gastric emptying
GEBT	gastric emptying breath test
GERD	gastroesophageal reflux disease
GHS1 α	Growth Hormone Secretagogue 1 α
GI	gastrointestinal
GLP-1	glucagon-like peptide-1
GP	gastroparesis
HbA1c	glycosylated hemoglobin A1c
HEOR	health economic outcomes research
HIPAA	Health Insurance Portability and Accountability Act
HR	heart rate
HRT	hormonal replacement therapy
ICF	informed consent form
ICH	International Council on Harmonisation
IEC	Independent Ethics Committee
IGF-1	insulin-like growth factor-1

IND	Investigational New Drug Application
INR	international normalized ratio
IRB	Institutional Review Board
IWRS	interactive web response system
MACE	Major Adverse Cardiovascular Events
MAR	missing at random
mITT	modified intent-to-treat
MMRM	mixed model for repeated measures
MSP	medical safety physician
NRS	numerical rating scale

QTcB	QT interval corrected for heart rate using the Bazett formula
QTcF	QT interval corrected for heart rate using Fridericia formula
RLM	relamorelin
SAE	serious adverse event
SAP	statistical analysis plan
SC	subcutaneous(ly)
SF-12v2	12-item Short Form Survey (version 2)
SGLT-2	Sodium glucose co-transporter 2
SMBG	self-monitoring of blood glucose
SoA	Schedule of Activities

SUSAR	suspected unexpected serious adverse reaction
T1DM	type 1 diabetes mellitus
T2DM	type 2 diabetes mellitus
ULN	upper limits of normal
US	United States of America
WOCBP	women of childbearing potential

